## 4.7.4. Special Safety Topics

In addition to general safety parameters, safety information on specific topics will also be presented. Additional special safety topics may be added as warranted. In general, for topics regarding safety in special groups and circumstances, patient profiles, patient listings, or both, where applicable, will be provided when needed to allow medical review of the time course of cases or events, related parameters, patient demographics, study drug treatment, and meaningful concomitant medication use. In addition to the safety topics for which provision or review of patient data is specified, these will be provided when summary data are insufficient to permit adequate understanding of the safety topic.

#### **4.7.4.1. Infections**

Completion of the Infection eCRF page is required for each infection reported as an AE or SAE.

Infections will be defined using the PTs from the MedDRA Infections and Infestations SOC. TE infections will be analyzed for

- all infections: TE infections by PT (by maximum severity)
- serious infections: TE infections by PT (by maximum severity)
- opportunistic infections (OI): TE OI by narrow terms and broad terms separately, and
- infections resulting in permanent study drug discontinuation.

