#### **Infections**

A participant should be permanently discontinued from study intervention if the participant

- develops active TB or HIV infection during the study
- has untreated **CCI** or
- becomes HBV DNA or HCV RNA positive as described in Sections 8.2.9 and 8.2.10.

The HBV DNA result is to be confirmed if initial positive test result is positive but below the level of quantification (Section 7.1.4). Prior to discontinuation of study intervention, the participant is to be referred to, evaluated, and managed by a specialist physician with expertise in evaluation and management of viral hepatitis. The timing of discontinuation from study intervention relative to the initiation of any antiviral treatment for hepatitis is to be based on the recommendation of the consulting specialist physician, in conjunction with the investigator, and aligned with medical guidelines and standard of care.

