## **Potential opportunistic infections**

The MedDRA terms used to identify infections considered to be OI in patients with immune mediated inflammatory conditions treated with immunomodulatory drugs are based on Winthrop et al. (2015) and are listed in the compound level safety standards. See also FVAA Protocol (Section 10.8, Appendix 8).

Potential opportunistic infections (POIs) will be identified in 2 ways:

- 1. POIs will be identified from TEAEs based on a Lilly-defined list of MedDRA PTs shown in Appendix 3, Section 6.3. The list is maintained outside the Study FVAA SAP and can be updated without an amendment to the Study FVAA SAP. These PTs are a subset of terms from the Infections and Infestations SOC, and
- 2. Medical will review the list of POIs, including the details captured on the infection-specific eCRF, and determine whether the infection is a 'confirmed opportunistic infection.'

The summary analysis of OIs identified using the 2 approaches above will be provided. Events will be ordered by decreasing frequency of pathogen nested under pathogen species (mycobacteria, bacteria, fungal, viral, and parasites). The order of frequency will be determined using the LY3972406 group.

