Fungal oesophagitis
Gastrointestinal candidiasis
Hepatic candidiasis
Hepatosplenic candidiasis
Meningitis candida
Mucocutaneous candidiasis
Oesophageal candidiasis
Oral candidiasis
Oral fungal infection
Oropharyngeal candidiasis
Peritoneal candidiasis
Respiratory moniliasis
Splenic candidiasis
Systemic candida
Coccidioides encephalitis
Coccidioidomycosis
Cutaneous coccidioidomycosis
Meningitis coccidioides
Cryptococcal cutaneous infection
Cryptococcal fungaemia
Cryptococcosis
Cryptococcus test
Cryptococcus test positive
Disseminated cryptococcosis
Gastroenteritis cryptococcal
Meningitis cryptococcal
Neurocryptococcosis
Osseous cryptococcosis
Pneumonia cryptococcal
Biliary tract infection cryptosporidial
Cryptosporidiosis infection
Gastroenteritis cryptosporidial
Cytomegalovirus chorioretinitis
Cytomegalovirus colitis
Cytomegalovirus duodenitis
Cytomegalovirus enteritis
Cytomegalovirus enterocolitis
Cytomegalovirus gastritis
Cytomegalovirus gastroenteritis
Cytomegalovirus gastrointestinal infection

Preferred Term (MedDRA Version 26.1)
Cytomegalovirus gastrointestinal ulcer
Cytomegalovirus hepatitis
Cytomegalovirus infection
Cytomegalovirus mononucleosis
Cytomegalovirus mucocutaneous ulcer
Cytomegalovirus myelomeningoradiculitis
Cytomegalovirus myocarditis
Cytomegalovirus nephritis
Cytomegalovirus oesophagitis
Cytomegalovirus pancreatitis
Cytomegalovirus pericarditis
Cytomegalovirus syndrome
Cytomegalovirus test
Cytomegalovirus test positive
Cytomegalovirus urinary tract infection
Cytomegalovirus viraemia
Disseminated cytomegaloviral infection
Encephalitis cytomegalovirus
Pneumonia cytomegaloviral
Asymptomatic viral hepatitis
Chronic hepatitis B
HBV-DNA polymerase increased
Hepatitis B
Hepatitis B antigen
Hepatitis B antigen positive
Hepatitis B core antigen
Hepatitis B core antigen positive
Hepatitis B DNA assay
Hepatitis B DNA assay positive
Hepatitis B DNA increased
Hepatitis B e antigen
Hepatitis B e antigen positive
Hepatitis B reactivation
Hepatitis B surface antigen
Hepatitis B surface antigen positive
Hepatitis B virus test
Hepatitis B virus test positive
Hepatitis post transfusion
Hepatitis viral
Withdrawal hepatitis

Preferred Term (MedDRA Version 26.1)
Chronic hepatitis C
Hepatitis C
Hepatitis C RNA
Hepatitis C RNA fluctuation
Hepatitis C RNA increased
Hepatitis C RNA positive
Hepatitis C virus test
Hepatitis C virus test positive
Colitis herpes
Eczema herpeticum
Gastritis herpes
Herpes oesophagitis
Herpes ophthalmic
Herpes sepsis
Herpes simplex

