Eye infection toxoplasmal
Meningitis toxoplasmal
Myocarditis toxoplasmal
Pneumonia toxoplasmal
Toxoplasma serology
Toxoplasma serology positive
Toxoplasmosis
American trypanosomiasis
Chagas' cardiomyopathy
Meningitis trypanosomal
Trypanosoma serology positive
Trypanosomiasis
Adrenal gland tuberculosis
Bone tuberculosis
Choroid tubercles
Conjunctivitis tuberculous
Cutaneous tuberculosis
Disseminated Bacillus Calmette-Guerin infection
Disseminated tuberculosis
Ear tuberculosis
Epididymitis tuberculous
Extrapulmonary tuberculosis
Immune reconstitution inflammatory syndrome associated tuberculosis
Interferon gamma release assay
Interferon gamma release assay positive
Intestinal tuberculosis
Joint tuberculosis
Lymph node tuberculosis
Male genital tract tuberculosis
Meningitis tuberculous
Mycobacterium tuberculosis complex test
Mycobacterium tuberculosis complex test positive
Oesophageal tuberculosis
Oral tuberculosis
Pericarditis tuberculous
Peritoneal tuberculosis

Preferred Term (MedDRA Version 26.1)
Prostatitis tuberculous
Pulmonary tuberculoma
Pulmonary tuberculosis
Renal tuberculosis
Salpingitis tuberculous
Silicotuberculosis
Spleen tuberculosis
Thyroid tuberculosis
Tuberculid
Tuberculin test
Tuberculin test false negative
Tuberculin test positive
Tuberculoma of central nervous system
Tuberculosis
Tuberculosis bladder
Tuberculosis gastrointestinal
Tuberculosis liver
Tuberculosis of central nervous system
Tuberculosis of eye
Tuberculosis of genitourinary system
Tuberculosis of intrathoracic lymph nodes
Tuberculosis of peripheral lymph nodes
Tuberculosis ureter
Tuberculous abscess central nervous system
Tuberculous endometritis
Tuberculous laryngitis
Tuberculous pleurisy
Tuberculous tenosynovitis
Vibrio test positive
Vibrio vulnificus infection

Abbreviations: HBV = hepatitis B virus; MedDRA = Medical Dictionary for Regulatory Activities.

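### SAP 4.7.4.1 defines infections by one MedDRA class and says the Appendix 3 list lies inside it, but about 73 listed terms are test names, so a confirmed opportunistic infection can be missing from the all-infections table

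*SAP*

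**What the plan says.** SAP 4.7.4.1 opens with the definition: "Infections will be defined using the PTs from the MedDRA Infections and Infestations SOC". Four treatment-emergent analyses follow: all infections, serious infections, opportunistic infections, and infections that led to permanent discontinuation of study drug.

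The next part of that section, on potential opportunistic infections (POIs), gives a different route in: "POIs will be identified from TEAEs based on a Lilly-defined list of MedDRA PTs shown in Appendix 3, Section 6.3". It then says of the listed preferred terms (PTs): "These PTs are a subset of terms from the Infections and Infestations SOC". A medical review decides which POIs are confirmed as opportunistic. On reporting, "The summary analysis of OIs identified using the 2 approaches above will be provided".

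Appendix 3 (SAP 6.3) includes "Hepatitis B DNA assay positive", "Hepatitis C RNA positive" and "Interferon gamma release assay positive".

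Protocol 7.1.3 places viral positivity under its Infections heading. Among the grounds for permanent discontinuation of study intervention is that the participant "becomes HBV DNA or HCV RNA positive as described in Sections 8.2.9 and 8.2.10".

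**The concern.** The SAP's description of its own list does not fit the list. A lung diffusion test, a silver stain or a viral DNA assay is a measurement, and its name does not read as an infection term. Two selection rules are therefore in force, and they do not select the same events.

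The consequence is a set of infection tables that need not nest. An event coded as a test result can enter the opportunistic summary from the list, be confirmed as opportunistic, and still be missing from the table of all infections. If a programmer instead reads the subset sentence as a restriction, the same event disappears from the opportunistic summary too. The count then depends on which sentence is programmed.

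This matters most for viral reactivation, which the protocol treats as an infection and which may be detected first by a laboratory test. Protocol 8.2.6 tells investigators to report clinically relevant laboratory changes as adverse events, so a test-coded report is possible.

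**Working it through.** The plan gives no figure to reproduce. The check is a count of terms, a trace of one event through each rule, and a look at how often such an event could arise.

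**1. Does the list lie inside the class?** Input: the term names in SAP 6.3. Counted were rows naming a test, assay, antigen, antibody index, nucleic acid result, serology, stain or function test rather than a disease.

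- Rows: 75. Two terms appear twice (JC polyomavirus test; JC polyomavirus test positive), so distinct terms = 75 − 2 = 73.
- Make-up: 46 contain the word test; 17 are hepatitis B or C antigen, DNA or RNA terms without that word; 10 are others (3 beta-D-glucan, 3 serology, 2 interferon gamma release assay, 1 antibody index, 1 stain). 46 + 17 + 10 = 73.
- Hepatitis B or C terms: the 17 above plus 4 virus-test terms = 21. Of these, 8 name HBV DNA or HCV RNA.
- Of the 73, 28 are bare test names with no result attached.

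The documents do not give the class of each term. That these terms lie outside Infections and Infestations is an inference from wording. It is clearest for the lung diffusion, silver stain and beta-D-glucan terms, which name no pathogen.

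**2. Where does a test-coded event go?** Take a treatment-emergent adverse event (TEAE) coded to the HBV DNA positive term.

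| Analysis | Rule available in the SAP | Result |
|---|---|---|
| All infections | Class only | Omitted |
| Serious infections | Class only | Omitted, even if serious |
| Infections leading to permanent discontinuation | Class only | Omitted, even if it led to discontinuation |
| Opportunistic infections | List match from TEAEs, then medical review | Included, unless the class statement is used as a filter |
| General TEAE tables and AEs leading to discontinuation (SAP 4.7.2) | All classes | Included |

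**3. How often could it arise?** From Protocol 1.3.1 and 1.3.2:

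- HBV DNA is tested after screening at Visit 9 (Week 12), early discontinuation (ED) and Visit 804, and only in participants positive for anti-HBc at screening.
- No HCV RNA test is scheduled after screening.
- A positive at Week 12 or ED, with onset dated to that visit, meets the TEAE definition in SAP 4.7.2. A first positive at Visit 804 is follow-up emergent, so it is outside the treatment-emergent tables whatever its class.
- Week 12 ends the treatment period and the ED visit follows the decision to stop. A scheduled test can therefore hardly be what causes permanent discontinuation. That case needs an unscheduled test, such as the hepatic evaluation in Protocol 8.2.11.

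**4. Size of one omission.** One missed case in an arm of n changes 1/n to 0. Arm sizes are redacted. Assuming n = 30, that is 1/30 = 3.3%; at half that size 1/15 = 6.7%, and at double 1/60 = 1.7%.

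**The case against.** A reader might infer that test-coded HBV DNA or HCV RNA positivity falls outside the infection analyses altogether. The documents do not support that. The POI rule starts from all TEAEs and matches them to a list that names these terms. No sentence tells the programmer to filter by class first; the subset sentence only describes the list. This part of the objection stands, and it limits the gap to the three class-based analyses.

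Nor are cases lost from safety reporting. SAP 4.7.2 tabulates TEAEs and AEs leading to permanent discontinuation by preferred term within class, and SAP 4.7.4.2 lists hepatic serology. That also stands.

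Protocol 10.3.4 asks for a diagnosis rather than individual signs or symptoms whenever possible, and Protocol Appendix 8 offers hepatitis B reactivation as an opportunistic infection. Many cases would then be coded to a disease term. This lowers the expected number but does not remove the problem, because Protocol 8.2.6 and 10.3.1 also allow a clinically significant laboratory result to be the reported event.

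Finally, defining all infections by a single class is a legitimate convention, and the count of 73 does not measure harm. Both are fair. The defect is that this convention is combined with a list that does not fit it and is said to be contained in it.

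**Conclusion.** The point holds in a limited form. The subset statement is wrong on the face of Appendix 3, and the class-only definition omits test-coded events from the all-infection, serious-infection and infection-related discontinuation analyses while the list can bring the same events into the opportunistic summary. The clearest example is HBV DNA positivity found at Week 12 and reported as a laboratory result.

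The expected number is small, possibly zero. The stronger reading, that participants stopped for viral positivity would routinely be missing from the discontinuation table, is not supported, because it needs an unscheduled test and a report coded as a test. The primary and secondary efficacy analyses are unaffected. The correction is still worth making, because one case can be the whole signal in a rare-event table and the tables should agree with each other.

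Two assumptions carry this: that the test-name terms are outside the class in MedDRA 26.1, and that some sites will report a result rather than a diagnosis.

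**What to change.** In SAP 4.7.4.1:

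- Check the class of the Appendix 3 terms against MedDRA 26.1, and delete the sentence calling the list a subset of Infections and Infestations.
- State that Appendix 3 is matched to all TEAEs regardless of class.
- Define a treatment-emergent infection as any TEAE whose preferred term is in the class, or is on the Appendix 3 list and is judged by blinded medical review to represent an infection, opportunistic or not. Use this definition in all four infection analyses.

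The review question has to be widened in this way. As planned, it decides only whether a POI is a confirmed opportunistic infection, so a genuine but non-opportunistic infection coded as a test would still be left out. The review step also keeps the 28 bare test names from being counted as infections without a judgement.

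The cost is SAP wording, one programming rule and slightly more medical review of test-coded events. No data collection or protocol change is needed. Reviewers may lack Infection eCRF details for an event that the site did not regard as an infection.

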## **Potential opportunistic infections**

The MedDRA terms used to identify infections considered to be OI in patients with immune mediated inflammatory conditions treated with immunomodulatory drugs are based on Winthrop et al. (2015) and are listed in the compound level safety standards. See also FVAA Protocol (Section 10.8, Appendix 8).

Potential opportunistic infections (POIs) will be identified in 2 ways:

- 1. POIs will be identified from TEAEs based on a Lilly-defined list of MedDRA PTs shown in Appendix 3, Section 6.3. The list is maintained outside the Study FVAA SAP and can be updated without an amendment to the Study FVAA SAP. These PTs are a subset of terms from the Infections and Infestations SOC, and
- 2. Medical will review the list of POIs, including the details captured on the infection-specific eCRF, and determine whether the infection is a 'confirmed opportunistic infection.'

The summary analysis of OIs identified using the 2 approaches above will be provided. Events will be ordered by decreasing frequency of pathogen nested under pathogen species (mycobacteria, bacteria, fungal, viral, and parasites). The order of frequency will be determined using the LY3972406 group.

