## Duration of the treatment period and post-treatment follow-up

The 12-week duration of the treatment period is appropriate for assessing efficacy based on achieving steady state concentrations after with LY3972406 and allowing sufficient time for pharmacological effects to occur. This duration is also supported by the toxicology data for LY3972406 available at the time this study was designed.

The post-treatment follow-up can be up to 12 weeks and is designed to capture any additional safety signals and assess time to potential relapse.

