#### 4.7.2. Adverse Events

AEs are recorded in the electronic case report forms (eCRFs). Where changes in severity are recorded in the eCRF, each separate severity of the AE will be reported in the listings. Only the most severe will be used in the summary tables.

AEs will be coded according to the current version at the time of database lock of the Medical Dictionary for Regulatory Activities (MedDRA). The MedDRA lowest level term will be used in defining which events are treatment-emergent (TE). The severity of AEs is recorded as mild, moderate, or severe. The maximum severity for each lowest level term during the baseline period will be used as baseline. Baseline for the double-blind treatment period is defined as all preexisting conditions recorded at Visit 1 and any AEs recorded before the first dose of study intervention. The treatment period will be included as postbaseline for the analysis. For events with a missing severity during the baseline period, it will be treated as 'mild' in severity for determining treatment-emergence. Events with a missing severity during the postbaseline period will be treated as 'severe,' and treatment-emergence will be determined by comparing to baseline severity. For events occurring on the day of first taking study medication, the start times of the study treatment and AE will be used to determine whether the event was pre- versus posttreatment. If the start time for the AE is missing, it will be assumed to have started in the later period.

A TEAE is defined as an event that first occurred or worsened in severity after baseline and on or prior to the date of the last visit within the treatment period. For each event classification term, the number of participants experiencing a TEAE with that classification term will be tabulated. A follow-up emergent AE is defined as an event that first occurred or worsened in severity after Week 12 (Visit 9) or early discontinuation. For events that are gender-specific, the denominator and computation of the percentage will include participants only from the given gender. A preexisting condition is defined as a condition that starts before the participant has provided written informed consent and is ongoing at consent. A non-TEAE is defined as an AE that starts after informed consent but prior to the first dose. Further definitions and information for AEs can be found in FVAA Protocol in Section 8.3 and in Appendix 3, Section 10.3.

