## 4.7.4.2. Hepatic Safety

Hepatic laboratory parameters include alanine aminotransferase, aspartate aminotransferase, total bilirubin, serum alkaline phosphatase, and gamma-glutamyltransferase. The central laboratory reference ranges will be used for these laboratory assessments.

If a participant experiences elevated laboratory parameters, as detailed in Section 8.2.11 of the FVAA Protocol, additional tests will be performed to confirm the abnormality. Additional safety data may be collected if required, as defined in the FVAA Protocol. Where applicable, the following will be presented.

The participants' liver disease history and associated person liver disease history data will be listed. Use of acetaminophen during the study, which has potential for hepatotoxicity, will be listed. Results from any hepatic monitoring procedures, such as a magnetic resonance elastography scan, and biopsy assessments will be listed, if performed.

Hepatic risk factor assessment data will be listed. Liver related signs and symptoms data will be summarized by population and treatment, if deemed appropriate, and listed. Alcohol and recreational drug use data will also be listed.

All hepatic chemistry, hematology, coagulation, and serology data will be listed. Values outside the reference ranges will be flagged on the individual participant data listings.

The number and percentage of participants with the following abnormal elevations in hepatic laboratory tests at any time will be summarized between treatment groups:

- an alanine aminotransferase or aspartate aminotransferase measurement of at least 3-fold, at least 5-fold, and at least 10-fold the central laboratory upper limit of normal during the treatment period
- a total bilirubin measurement of at least 2-fold the central laboratory upper limit of normal during the treatment period, and
- an alkaline phosphatase measurement of at least 2.5-fold the central laboratory upper limit of normal during the treatment period.

The number and percentage of participants reporting hepatic events will be assessed using the MedDRA PTs contained in the following Standardized MedDRA Queries (SMQs):

- Broad and narrow terms in the Liver-related investigations, signs and symptoms SMQ
- Broad and narrow terms in the Cholestasis and jaundice of hepatic origin SMQ
- Broad and narrow terms in the Hepatitis noninfectious SMQ

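### Opportunistic-infection and liver-threshold counts stop at the last treatment-period visit, so cases first arising in follow-up are left out of those two by-arm analyses

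*SAP*

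**What the plan says.** SAP 4.7.4.1 analyses opportunistic infections as treatment-emergent: "opportunistic infections (OI): TE OI by narrow terms and broad terms separately". It names two ways of identifying potential opportunistic infections (POIs). The first is that "POIs will be identified from TEAEs based on a Lilly-defined list of MedDRA PTs shown in Appendix 3, Section 6.3". The second works on the output of the first: "Medical will review the list of POIs, including the details captured on the infection-specific eCRF", and it decides which entries are confirmed.

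SAP 4.7.2 sets the windows. A TEAE first occurs or worsens "after baseline and on or prior to the date of the last visit within the treatment period". Anything later belongs to another class: "A follow-up emergent AE is defined as an event that first occurred or worsened in severity after Week 12 (Visit 9) or early discontinuation".

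SAP 4.7.4.2 counts participants with ALT or AST "at least 3-fold, at least 5-fold, and at least 10-fold the central laboratory upper limit of normal during the treatment period". The bilirubin (2-fold) and ALP (2.5-fold) bullets carry the same restriction. The sentence that introduces the three bullets, however, speaks of elevations at any time.

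Protocol 4.2 says that the follow-up of up to 12 weeks "is designed to capture any additional safety signals and assess time to potential relapse". The follow-up schedule (Protocol 1.3.2) collects AEs, hematology and chemistry at Visits 801 to 804. It collects HBV DNA at the ED visit and Visit 804 in participants who were anti-HBc positive at screening.

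**The concern.** Opportunistic infection and hepatic safety each have their own subsection among the special safety topics in the SAP. For both, the protocol collects follow-up data that the headline counts do not use. For completers a dose is observed at Visit 9, so the counting window closes on a dosing day with no carry-over period.

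The liver counts are the more exposed of the two. Under Protocol 7.1.1 and 7.1.3, stopping study intervention for a liver abnormality ends the treatment period, while Protocol 8.2.11 continues monitoring until values normalize or approach baseline. A value that is still rising at discontinuation can therefore peak after counting has stopped.

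This is the compound's first study in psoriasis patients, and its data will inform further development. A table of confirmed opportunistic infections or of 10-fold ALT/AST elevations could show zero while such a case sits in the database.

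**Working it through.** The plan gives no figure to reproduce. The check sets the analysis windows against the collection schedule and counts visits.

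**1. Opportunistic infections.** Route 1 takes TEAEs that match the term list. Route 2 reviews the route 1 list, so it can confirm or reject entries but cannot add any. An infection that starts after Visit 9 or the ED visit is a follow-up emergent AE, so it enters neither route. For example, HBV reactivation is listed in Protocol Appendix 8 and in SAP Appendix 3. If first detected at Visit 804 and reported as an AE, it would match the term list by name, but the list would not be run on it.

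**2. Liver thresholds.** All three bullets stop at the end of the treatment period. The SAP gives no separate laboratory definition of that period, so I assume that it ends at Visit 9 or ED, as for AEs. Take a hypothetical participant at 4 times the upper limit of normal (ULN) for ALT at the ED visit, who reaches 11 times afterwards. As the bullets stand, this participant counts in the 3-fold row only (4 ≥ 3, 4 < 5). With follow-up counted, the 11-fold value meets the 3-, 5- and 10-fold limits.

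**3. What follow-up reporting is named.** SAP 4.7 promises separate follow-up summaries without giving their content. SAP 4.7.2 names follow-up emergent AEs, SAEs including deaths, and AEs leading to study discontinuation. Neither names an opportunistic-infection classification or a liver-threshold count. SAP 4.7.6 makes listing without summary the default for safety assessments not detailed in that section.

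**4. Size, for a completer.** On treatment there are 12 weeks and 7 post-baseline chemistry visits (Visits 3 to 9). Follow-up adds up to 12 weeks and up to 4 visits (801 to 804). Visits 803 and 804 take place only if PASI at the preceding visit is below baseline, so the share depends on where follow-up ends:

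- Visit 804: 12/(12+12) = 12/24 = 50% of weeks; 4/(7+4) = 4/11 = 36% of chemistry visits.
- Visit 803: 8/(12+8) = 8/20 = 40% of weeks; 3/(7+3) = 3/10 = 30% of visits.
- Visit 802: 4/(12+4) = 4/16 = 25% of weeks; 2/(7+2) = 2/9 = 22% of visits.

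For an anti-HBc-positive completer who reaches Visit 804, 1 of the 2 scheduled post-baseline HBV DNA tests (Visits 9 and 804) falls outside. Early discontinuers have a shorter treatment period, so these fractions do not carry over to them.

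**The case against.** The strongest reply is that follow-up is already covered. SAP 4.7 plans separate follow-up summaries, and an HBV reactivation reported as an AE at Visit 804 would appear in the follow-up AE table under its own preferred term. All hepatic chemistry and serology is listed, with out-of-range values flagged and no period limit. The counts of hepatic events by standardized MedDRA query (SMQ) also state no period limit. The Infection eCRF is required for every infection reported as an AE or SAE. Protocol Appendix 8 says that the sponsor will categorize infections as opportunistic for analysis, without restricting this to TEAEs. SAP 4.7.4 allows patient profiles where summaries are insufficient.

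Most of this stands. A reader might infer that late cases disappear from reporting, or that hepatic safety as a whole covers only half the observation time. The documents support neither. What is missing is the opportunistic-infection classification and the threshold count by arm, which listings and discretionary profiles do not supply.

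A reader might also infer that the risk estimate is biased downward. That is not shown. The tables are labelled as treatment-emergent or treatment-period, and separating on-treatment from off-drug events is a legitimate choice. The public text gives no half-life or carry-over figure to show how much of follow-up belongs to the drug's risk.

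Finally, the cut-off is the last treatment-period visit and not the final dose. For an early discontinuer, an event between the last dose and the ED visit may still be a TEAE.

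**Conclusion.** The point holds in limited form. As written, the SAP leaves opportunistic infections and liver-test peaks that first arise after Visit 9 or ED out of the two by-arm counts meant to show them. This follows from stated rules and is not merely missing detail. The liver subsection also contradicts itself on its window.

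The uncounted part for a completer is at most 12 of 24 weeks and 4 of 11 scheduled chemistry visits, and 2 of 9 visits if follow-up ends at Visit 802. The HBV example is narrow: it needs an anti-HBc-positive participant who reaches Visit 804, so few cases are likely. Liver values that peak after discontinuation are the more practical worry.

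The conclusion assumes that the treatment period for laboratory counts ends where the TEAE window ends. If the wider wording of the lead-in sentence was intended, the liver half becomes a wording correction and the infection half remains. Primary and secondary efficacy analyses are unaffected, and no data are lost.

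**What to change.** - **SAP 4.7.4.1:** apply the POI term list and the medical confirmation to follow-up emergent AEs as well as TEAEs. Tabulate follow-up emergent opportunistic infections by arm, separately from the treatment-emergent ones.
- **SAP 4.7.4.2:** make the introductory sentence and the three bullets agree on the window. Keep the treatment-period counts and add the same threshold counts for follow-up, using Visits 801 to 804 and any repeat central laboratory values, labelled as off-drug.
- **Denominators:** state how many participants in each arm contribute follow-up data, since attendance at Visits 803 and 804 depends on PASI.

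The cost is SAP wording, a few extra tables and a small amount of added medical review. No new visits or samples are needed, and the treatment-period tables do not change. The change is best made before unblinding.
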